Appendix 2 Pharmacokinetics, Immunogenicity, and Pharmacodynamic Sample Collection Schedule

Table 9 Pharmacokinetic, Immunogenicity, and Pharmacodynamic Sampling Schedule: Part 1A

Study Day	Time Point	Window	PK (Serum) ^a	ADA to MGD020 (Serum)	Cytokines (Serum)	PD: T-cell Binding & Phenotype (Whole Blood)	PD: IPDA (PBMCs)	HLA Typing (Whole Blood)
-56 to -1	Screening	N/A		X				
1	Pre-MGD020 infusion	N/A	X		X	X	X	X
1	EOI MGD020	+ 10 min	X					
1	1 h after EOI MGD020	± 5 min	X		X	X		
1	4 h after EOI MGD020	± 5 min	X		X	X		
2	No specific time	N/A	X		X	X		
3	No specific time	N/A	X					
8	No specific time	± 2 days	X		X	X		
15	No specific time	± 2 days	X	X				
22	No specific time	± 2 days	X					
29	No specific time	± 2 days	X	X				
IRR-CRS ^b	No specific time ^b	N/A	X	X	X			
43/EOS	EOS	± 3 days	X	X			X	

a Obtain pre-infusion PK samples before start of infusion on visit day (dosing day) or day before. When collecting multiple samples, collect PK sample first.

b PK, ADA, and cytokine samples may be obtained selectively at additional time points in participants who experience signs and symptoms of IRR or CRS.

Abbreviations: ADA: anti-drug antibody; CRS: cytokine release syndrome; EOI: end of infusion; EOS: end of study; HLA: human leukocyte antigen; IPDA:

intact proviral DNA assay; IRR: infusion related reaction; N/A: not applicable; PBMC: peripheral blood mononuclear cell; PD: pharmacodynamic;

PK: pharmacokinetic.

Table 10 Pharmacokinetic, Immunogenicity, and Pharmacodynamic Sampling Schedule: Part 1B

Study Day	Time Point	Window	PK ^a (Serum)		ADA (Serum)		Cytokines (Serum)	PD: T-cell Binding & Phenotype (Whole Blood)	PD: IPDA (PBMCs)	HLA Typing (Whole Blood)
			MGD020	MGD014	MGD020	MGD014				
-56 to -1	Screening	N/A			X ^b	X ^b				
1	Pre-MGD020 infusion	N/A	X	X			X	X	X	X
1	EOI MGD020	+ 10 min	X							
1	EOI MGD014	+ 10 min		X						
1	1 h after EOI MGD014	± 5 min	X	X			X	X		
1	4 h after EOI MGD014	± 5 min	X	X			X	X		
2	No specific time	N/A	X	X			X	X		
3	No specific time	N/A	X	X						
8	No specific time	± 2 days	X	X			X	X		
15	No specific time	± 2 days	X	X	X	X				
22	No specific time	± 2 days	X	X						
29	No specific time	± 2 days	X	X	X	X				
IRR-CRS ^c	No specific time ^c	N/A	X	X	X	X	X			
43/EOS	End of study	± 3 days	X	X	X	X			X	

a Obtain pre-infusion PK samples before start of infusion on visit day (dosing day) or day before. When collecting multiple samples, collect PK sample first.

b For participants who have been previously exposed to MGD014 or MGD020, obtain screening samples for ADA (MGD014 and MGD020) at least 21 days prior to enrollment to allow for results to be reported before enrollment.

c PK, ADA and cytokine samples may be obtained selectively at additional time points in participants who experience signs and symptoms of IRR or CRS.

Abbreviations: ADA: anti-drug antibody; CRS: cytokine release syndrome; EOI: end of infusion; EOS: end of study; HLA: human leukocyte antigen; IPDA: intact proviral DNA assay; IRR: infusion related reaction; N/A: not applicable; PBMC: peripheral blood mononuclear cell; PD: pharmacodynamic; PK: pharmacokinetic.

Table 11 Pharmacokinetic, Immunogenicity, and Pharmacodynamic Sampling Schedule: Part 2

Study Day	Time Point	Window	PK ^a (Serum)		ADA (Serum)		Cytokines (Serum)	PD: T-cell Binding & Phenotype (Whole Blood)	PD: IPDA & rca- RNA (PBMCs)	HLA Typing (Whole Blood)	PD: QVOA (Leuka- pheresis)	PD: SCA (Plasma)
			MGD020	MGD014	MGD020	MGD014						
-56 to -1	Screening	N/A			X ^b	X ^b					X ^c	
1	Pre-MGD020 infusion	N/A	X	X			X	X	X	X		X
1	EOI MGD020	+ 10 min	X									
1	EOI MGD014	+ 10 min		X								
1	1 h after EOI MGD014	± 5 min	X	X			X	X				
1	4 h after EOI MGD014	± 5 min	X	X			X	X				
2	No specific time	N/A	X	X			X	X				
4	No specific time	N/A	X	X								
8	No specific time	± 1 day	X	X			X	X				
15	Pre-MGD020 infusion	N/A	X	X	X	X	X	X				
15	EOI MGD020	+ 10 min	X									
15	EOI MGD014	+ 10 min		X								
15	4 h after EOI MGD014	± 5 min	X	X			X	X				
29	Pre-MGD020 infusion	N/A	X	X	X	X	X	X				
29	EOI MGD020	+ 10 min	X									
29	EOI MGD014	+ 10 min		X								
29	4 h after EOI MGD014	± 5 min	X	X			X	X				
43	No specific time	± 2 days	X	X					X		X ^c	X
50	No specific time	± 2 days	X	X								
64	No specific time	± 3 days	X	X								
IRR-CRS ^d	No specific time ^d	N/A	X	X	X	X	X					
78/EOS	EOS	± 3 days	X	X	X	X						X

a Obtain pre-infusion PK samples before start of infusion on visit day (dosing day) or day before. When collecting multiple samples, collect PK sample first.

b For participants who have been previously exposed to MGD014 or MGD020, obtain screening samples for ADA (MGD014 and MGD020) at least 21 days prior to enrollment to allow for results to be reported before enrollment.

c Optional leukapheresis is performed only after the participant is enrolled in the study. If the participant consents to this optional procedure, a baseline leukapheresis is completed. If a baseline leukapheresis was performed, a second leukapheresis procedure is completed 2 weeks (+2 week window) following the final study drug infusion.

d PK, ADA, and cytokine samples may be obtained selectively at additional time points in participants who experience signs and symptoms of IRR or CRS.

Abbreviations: ADA: anti-drug antibody; CRS: cytokine release syndrome; EOI: end of infusion; EOS: end of study; HLA: human leukocyte antigen; IPDA: intact proviral DNA assay; IRR: infusion related reaction; N/A: not applicable; PBMC: peripheral blood mononuclear cell; PD: pharmacodynamic; PK: pharmacokinetic; QVOA: quantitative viral outgrowth assay; rca-RNA: resting CD4+ T-cell-associated HIV-1 gag RNA; SCA: single copy assay.

TLFs	tables, listings, and figures			
t _{1/2}	terminal half-life			

T _{max}	time to maximal concentration
V_{ss}	steady-state volume of distribution

1 INTRODUCTION

This statistical analysis plan (SAP) provides a detailed and comprehensive description for the analysis of the study CP-MGD020-01 titled "A Phase 1 Study of MGD020 as a Single Agent or in combination with MGD014 in Persons with HIV-1 on Antiretroviral Therapy". This SAP Version 2.0 incorporates changes made in CP-MGD020-01 Protocol Amendment 1 and describes in detail the statistical methods to be used for analysis of the primary, secondary, and exploratory objectives to be collected from this study.

2 STUDY OBJECTIVES

2.1 Primary Objectives

The objective of this study is to characterize safety and tolerability of MGD020 as a single agent and in combination with MGD014.

2.2 Secondary Objectives

- Assess pharmacokinetics (PK) and immunogenicity (anti-drug antibody [ADA]) of MGD020.
- Assess PK and immunogenicity (ADA) of MGD014.
- Assess serum cytokine levels.

2.3 Exploratory Objectives

- Explore T-cell binding.
- Explore immunologic responses.
- Explore markers of persistent HIV-1.
- Explore correlations between virologic and immunologic markers.

Results of exploratory objectives may not be included in the clinical study report (CSR) unless they represent meaningful findings.

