3.3 Exploratory Objectives

Results of exploratory objectives may not be included in the clinical study report (CSR) unless they represent meaningful findings.

Exploratory Objective	Outcome or Endpoint
Explore T-cell binding	1. Percentages of peripheral CD4 and CD8 T cells with study drug bound over time
Explore immunologic responses	1. Changes in markers of activation or exhaustion on peripheral CD4 and CD8 T cells over time
Explore markers of persistent HIV-1	1. Changes in frequency of resting CD4+ T-cell infection by QVOA and/or IPDA 2. Changes in levels of rca-RNA 3. Changes in levels of residual low-level HIV-1 viremia quantified by SCA
Explore correlations between virologic and immunologic markers	1. Association between changes in immunologic and virologic markers

Abbreviations: CD: cluster of differentiation; HIV-1: human immunodeficiency virus-1; IPDA: intact proviral DNA assay; QVOA: quantitative viral outgrowth assay; rca-RNA: resting CD4+ T-cell-associated HIV-1 gag RNA; RNA: ribonucleic acid; SCA: single copy assay.

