4.9 Exploratory Endpoints and Analyses

The endpoints described in Sections 4.12.2-4.12.7 below are exploratory and only include participants from one or multiple parts of the study. The described analyses of these endpoints are optional and may not be performed if sample size does not permit.

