4.12.4 Quantitative Viral Outgrowth Assay (QVOA)

In Part 2 only, for participants who complete the optional leukapheresis, changes in pre- and post-dose measurements of the frequency of resting CD4+ T-cell infection by QVOA will be assessed. Data will be reported as infectious units per million (IUPM) and 95% CI values will be determined from the maximum likelihood method. Statistical significance of changes in QVOA values following dosing will be evaluated by a nonparametric 2-sided exact sign test. The exact sign test used for this analysis makes minimal statistical assumptions and is based solely upon whether IUPM values decrease following dosing. As QVOA is a robust and reproducible assay, declines of more than 50% in QVOA values from serial measurements are infrequently seen and would be suggestive evidence for HIV-1 reservoir depletion.

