4.12.5 Intact Proviral Deoxyribonucleic Acid Assay (IPDA)

In Parts 1A, 1B and 2, pre- and post-dose measurements of the frequencies of resting CD4+ T-cell infection by IPDA will be analyzed. Data will be reported as intact HIV-1 provirus per million CD4+ T-cells. 95% CIs for IPDA values will be determined and the statistical significance of changes following dosing will be evaluated by a nonparametric 2-sided exact sign test. Like QVOA, declines of more than 50% in IPDA values from serial measurements would be suggestive evidence for HIV-1 reservoir depletion.

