4.12.6 Resting CD4+ T-Cell-Associated HIV-1 gag RNA

In Part 2 only, changes in pre- and post-dose measurements of rca-RNA will be assessed. TATA binding protein RNA will be used as the reference to normalize HIV gene expression given its reported stability across treatment conditions. Data will be log-transformed and Wilcoxon Two-Sample test will be used for statistical analysis of rca-RNA of pre- and post-DART treatment as previously reported.

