5 LIST OF TABLES, LISTINGS, AND FIGURES

The list of tables, listings, and figures (TLFs) and associated shells planned for the CSR based on the analyses described in this SAP will be provided in a separate SPP, which will also include data reporting conventions and programming specifications for the development of these TLFs. Note that the SPP will not include TLF shells for the exploratory analyses described in Sections 4.12.2-4.12.7 as they will be performed and reported separately.

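### Exploratory results may be left out of the study report unless they are *meaningful*, an undefined, result-dependent condition that covers four planned significance tests on persistent HIV-1

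*SAP*

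**What the plan says.** The reporting rule is in SAP 2.3: "Results of exploratory objectives may not be included in the clinical study report (CSR) unless they represent meaningful findings". Protocol 3.3 sets the same condition, "unless they represent meaningful findings". Neither document says what makes a finding meaningful.

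One of the objectives under this rule is "Explore markers of persistent HIV-1". The SAP plans a significance test for each of four such markers:

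- QVOA (SAP 4.12.4; Part 2, participants who complete optional leukapheresis): "Statistical significance of changes in QVOA values following dosing will be evaluated by a nonparametric 2-sided exact sign test".
- IPDA (SAP 4.12.5; Parts 1A, 1B and 2): "the statistical significance of changes following dosing will be evaluated by a nonparametric 2-sided exact sign test".
- rca-RNA (SAP 4.12.6; Part 2): "Data will be log-transformed and Wilcoxon Two-Sample test will be used for statistical analysis of rca-RNA".
- SCA (SAP 4.12.7; Part 2): a two-sided exact sign test, as for IPDA.

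No alpha and no multiplicity rule is given for these tests. SAP 4.3 also says that no inferential statistics will be calculated, which does not fit these four sections.

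Two other statements bear on reporting. SAP 4.9, on the analyses in 4.12.2 to 4.12.7, says: "The described analyses of these endpoints are optional and may not be performed if sample size does not permit". SAP 5 explains that the programming plan will hold no table shells for the same analyses, "as they will be performed and reported separately".

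**The concern.** A rule that ties inclusion in the main report to what the result shows permits selective reporting. The protocol lists efficacy as not applicable, so these assays are the trial's only direct evidence on whether the drugs deplete persistent HIV-1. If one of several tests appears in the CSR and the others do not, the reader cannot see the denominator, and a chance result among unreported nulls looks the same as a real signal.

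Null results are a realistic outcome. Protocol 2.3.1.2.2 reports that MGD020 did not lower cell-associated viral RNA or delay rebound in SHIV-infected macaques on long-term ART, and Protocol 10.3.4 claims only a possibility of depletion. The rule therefore allows omission of the results that are most likely to occur.

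**Working it through.** **1. The text.** *May not be included* can mean *might be left out* or *must be left out*. On the first reading a result that is not meaningful can be dropped; on the second it has to be. On both, the result governs inclusion. The only benchmark nearby is a decline of more than 50%, for QVOA and IPDA (SAP 4.12.4 and 4.12.5). It is called suggestive evidence and is not linked to the word *meaningful* or to CSR inclusion.

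**2. Sample size.** The plan's own figure reproduces from SAP 4.3. Part 1A: 3 × (1 + 3) + 3 × (3 + 3) = 30. Part 1B: 3 × (3 + 3) = 18. Part 2: up to 6. Total: 30 + 18 + 6 = 54. QVOA, rca-RNA and SCA are limited to Part 2, so to at most 6 participants.

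**3. Attained size of each test.** Alpha 0.05 is assumed; the documents state none.

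- Sign test, n untied pairs, smallest two-sided p = 2 × 0.5^n. For n = 6 this is 0.03125; the next p at n = 6 is 0.21875, so the attained size is 0.03125. For n = 5 the smallest p is 0.0625, so the size is 0. QVOA and SCA can therefore reach 0.05 only if six untied pairs all move the same way.
- Two-sample Wilcoxon, 6 against 6 independent values: the largest two-sided size not above 0.05 is 38/924 = 0.0411.
- The pre and post values come from the same participants, so the independent-sample size does not hold if they are correlated. Simulating six bivariate normal pairs with the same rejection region gives:

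| Pre/post correlation (assumed) | Wilcoxon size |
|---|---|
| 0 | 0.041 |
| 0.3 | 0.020 |
| 0.5 | 0.011 |
| 0.7 | 0.004 |
| 0.9 | 0.0004 |

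**4. Chance of at least one nominally significant result under no effect.** The formula is 1 − Π(1 − size), assuming independent tests and n = 6 for every test.

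- All four tests, correlation 0: 1 − 0.96875³ × 0.9589 = 0.128.
- All four tests, correlation 0.7: 1 − 0.96875³ × 0.996 = 0.094.
- Wilcoxon contributing nothing: 1 − 0.96875³ = 0.091.
- QVOA and SCA both with fewer than six untied pairs (size 0), correlation 0: 1 − 0.96875 × 0.9589 = 0.071.
- The same, correlation 0.7: 1 − 0.96875 × 0.996 = 0.035.
- The same, Wilcoxon contributing nothing: 0.031.

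The ranges are about 9% to 13%, and about 3% to 7%. The sign tests are two-sided, so half of their false positives would be increases in the marker, not depletion.

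**5. IPDA.** It is planned in all three parts and is not confined to n = 6. The documents do not say whether parts are pooled. The sign-test size is 0.039 at n = 12, 0.031 at n = 18, 0.043 at n = 30 and 0.040 at n = 54. Putting the largest of these in place of 0.03125 in the first line of step 4 gives 1 − 0.96875² × 0.9572 × 0.9589 = 0.139, so the upper end moves little.

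**The case against.** The strongest defence is SAP 5. It says without any condition on the result that these analyses will be carried out and reported apart from the main tables, and the *meaningful* sentence limits only the CSR. A reader might infer that nothing at all commits the sponsor to reporting nulls; that goes too far. What remains is narrower: no venue is named and no completeness is promised.

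A reader might also take SAP 4.9 as a second result-dependent filter. It is not: the condition it states is sample size.

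A third tempting inference is that a test with p < 0.05 would be reported and the others dropped. No section equates *meaningful* with statistical significance. The 13% figure is also the upper end of an illustrative range: it needs zero pre/post correlation in the Wilcoxon test, full Part 2 enrolment, leukapheresis in all six participants and no ties.

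It is also fair to say that the endpoints are exploratory, that the rule is disclosed in advance, and that permission to omit does not show that anything will be omitted. These points limit the weight of the concern. They do not remove a result-dependent rule from the text.

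**Conclusion.** The concern holds in this form: both documents let exploratory results be left out of the CSR on an undefined, result-dependent criterion. The criterion covers four planned reservoir tests, and the promise of separate reporting names no place and does not extend to every result.

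The conclusion rests on the wording and not on the probabilities. Those are for scale only: about 9% to 13%, or about 3% to 7% if QVOA and SCA both fall short of six untied pairs. They assume alpha 0.05, n = 6 for every test, untied pairs for the remaining sign tests, and independent tests. The documents state no alpha and give no correlations. The four markers may well be correlated with each other, which would change the figures.

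The sponsor should correct this, but it does not threaten the trial. Primary safety and secondary PK, ADA and cytokine results are untouched.

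**What to change.** In SAP 2.3 and Protocol 3.3, delete the *meaningful findings* condition and state instead: every persistent-HIV-1 marker analysis performed (QVOA, IPDA, rca-RNA, SCA) will be reported regardless of result, in the CSR, an appendix or a named separate report cited in the CSR; any such analysis not performed will be listed with the reason. In SAP 5, name the separate report if that route is chosen. The option in SAP 4.9 to skip an analysis for lack of sample size can stay, provided the reason is recorded.

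Cost: one sentence in each document and a small amount of extra table programming, because the programming plan has no shells for these analyses. No new data are needed. Limiting the commitment to the persistent-HIV-1 markers avoids a larger programming task for T-cell binding, phenotype panels and marker correlations.

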3 STUDY DESIGN AND PLAN

3.1 Overall Study Design and Plan

This is a Phase 1, open-label study of MGD020 as a single agent or in combination with MGD014 in persons with HIV-1 (PWH) on antiretroviral therapy (ART). The study is designed to characterize the safety, tolerability, PK, immunogenicity, and pharmacodynamics (PD) of the study drugs. The study consists of 3 parts (Part 1A, Part 1B, and Part 2). In all parts, the participant's standard of care ART regimen is continued throughout the study period.

3.2 Part 1A – Single Ascending Dose of MGD020

Part 1A evaluates single ascending doses of MGD020 with a 1+3 design for cohorts 1–3 and 3+3 design for cohorts 4–6. A 2-week dose-limiting toxicity (DLT) period is observed prior to escalation to the next cohort level.

Part 1A has 6 cohorts. For cohorts 1–3, each cohort consists of 1 participant, unless a DLT occurs, which prompts expansion of the cohort to add an additional 3 participants. For cohorts 4–6, each cohort consists of 3 participants, with at least 24 hours between dosing of each participant within the cohort. If a DLT is experienced in 1 of the 3 participants in the cohort, the cohort will be expanded to add 3 additional participants. If one or more of the additional 3 participants treated at any given dose level also experiences a DLT, then that dose level will be defined as exceeding the maximum tolerated dose (MTD). The MTD will then be defined as the next lower dose level of MGD020. Escalation proceeds until either the MTD or maximum administered dose (MAD) is determined.

3.3 Part 1B – Single Ascending Dose of MGD020 and Fixed-dose of MGD014

Part 1B commences only after MTD or MAD of single-agent MGD020 has been determined in Part 1A. During Part 1B, participants will be enrolled and treated with a single ascending dose of MGD020 in combination with a fixed dose of 300 mcg/kg of MGD014.

MGD020 and MGD014 will be administered at the doses shown in the table below using a 3+3 design, beginning with Cohort 1, with at least 72 hours between dosing of each participant within a cohort. The first cohort will be treated with a single dose of MGD020 at a dose determined to be 1 dose level lower than MTD/MAD from Part 1A. MGD014 is dosed at 300 mcg/kg. Escalation to the next cohort follows the prespecified escalation rules.

MGD020 and MGD014 Combination Dose Escalation Scheme

Cohort	MGD020 a (mcg/kg)	MGD014 (mcg/kg)	Design
-1 ^b	MGD020 MTD/MAD -2	300	3+3
1	MGD020 MTD/MAD -1	300	3+3
2	MGD020 MTD/MAD	300	3+3

- a The MGD020 dose is determined by the single-agent MTD or MAD in Part 1A; the MGD020 dose in Cohort 1 will be one dose below the single-agent MTD/MAD (i.e., MTD/MAD -1).
- b If the dose level in Cohort 1 exceeds the MTD, de-escalation to Cohort -1 dose levels (MTD/MAD -2) may be considered.

Participants who completed Part 1A may be considered for enrollment in Part 1B, provided they meet all eligibility criteria, did not experience DLT in Part 1A, and do not have detectable ADA against MGD014 and/or MGD020 at the completion of Part 1A.

3.4 Part 2 – Multi-Dose Expansion Cohort

Part 2 commences only after an MTD or MAD of MGD020 in combination with MGD014 has been determined in Part 1B. Part 2 is a multi-dose expansion cohort with sequential infusions of a fixed dose of MGD020 in combination with a fixed dose of MGD014 administered every 2 weeks (Q2W) for 3 combination doses over 4 weeks. MGD020 is dosed at the MTD/MAD determined in Part 1B. MGD014 is dosed at 300 mcg/kg.

Up to 6 participants may enroll in Part 2 using a conventional 3+3 design. If 2 or more participants in the cohort of 6 experience a DLT, enrollment and further dosing of ongoing participants will be suspended pending further assessment of safety data.

Participants who completed Part 1 may be considered for enrollment in Part 2, provided they meet all eligibility criteria, did not experience DLT in Part 1, and do not have detectable ADA against MGD014 and/or MGD020 at the completion of Part 1.

4 STATISTICAL METHODOLOGY

4.1 General Considerations

The majority of the statistical summaries for this Phase 1 study will be descriptive. Summary statistics will consist of absolute and relative frequencies of each category of discrete variables of means, standard deviations, coefficient of variations, medians, and minimum and maximum values of continuous variables.

All data summaries and tabulations will be conducted using SAS® software Version 9.4 or higher.

4.2 Missing Data

Data that are reported as missing will be treated as missing in all data summaries. Imputation rules for partially recorded dates, in case that the complete dates are required to perform an analysis, will be provided in the Statistical Programming Plan (SPP). In descriptive summaries for safety, observations that are spurious (extreme relative to the majority of the data) will not be altered or removed from the summary.

